2.6.6 Subgroup analysis

Subgroup analysis for the secondary endpoints (1), (2), (3) and (5) will also be performed similarly as described in [Section 2.5.5](#) for the primary endpoint based on pre-defined subgroups ([Section 2.2.1](#)).

For secondary endpoint (4), subgroup analysis will be performed following a similar modeling as used for primary analysis of this endpoint ([Section 2.6.2](#)). Specifically, a negative binomial regression with Weibull baseline intensity function will be fitted within each subgroup with randomized treatment, STEMI/NSTEMI, PCI use at baseline and region as factors having fixed effects. P-value for treatment-subgroup interaction will be reported based on the same model but including factors for subgroup and treatment-subgroup interaction fitted to the overall population. Additionally, for descriptive purposes, exposure adjusted incidence rate and 95% CI for the secondary events will be reported by treatment group for each subgroup.

All the subgroup analyses for secondary endpoints will be performed for patients in FAS only.

2.7 Safety analyses

All safety analyses will be carried out for the Safety set (SAF).

2.7.1 Adverse events (AEs)

The following safety data will be collected and reported in this study for the double-blind period:

- all adverse events,
- all serious adverse events,
- adverse events of special interest (angioedema, hyperkalemia, hypotension, renal impairment, cognitive impairment, hepatotoxicity, statin drug-drug interaction, hypersensitivity, anaphylaxis, malignancy, embryo-fetal toxicity/lethality and neonatal/infantile toxicity through exposure from breast milk)
- adverse events leading to a change in dose (down titration), interruption or discontinuation of study drugs
- AEs occurred in the specific treatment phases are described in Table 2-5. AEs/ SAEs occurred during screening and double blind period will be summarized.

Table 2-5 Allocation of AEs

Screening epoch (V1-V101)	Double-blind treatment epoch		Phase AE to be reported in
	Randomization - EOT (V101-EOT)	EOT – EOS (EOT-V199)	
X			Reported by site from informed consent
	X		Report AE in double-blind period
X	X2		Report as two separate AEs: One with onset date X (X) during screening epoch and one with onset date X2 for DB
	X, X2		Report as one AE: One with onset date X during DB
		X	Report AE in post-EOT phase
		X, X2	Report as one AE: One with onset date X after EOT
	X	X2	Report as one AE in summaries for double-blind treatment epoch. For other summaries, report as two separate AEs; One with onset date X before EOT and one with onset date X2 during post-EOT
X indicates onset date of an AE. X2 stands for the same AE but with increased severity			

The number (and proportion) of patients with treatment emergent adverse events (events started after the first dose of study medication or events present prior to start of double-blind treatment but increased in severity based on preferred term) will be summarized in the following ways:

- by treatment, primary System Organ Class (SOC) and Preferred Term (PT).
- by treatment, primary System Organ Class (SOC), Preferred Term (PT) and maximum severity.
- by treatment, Standardized MedDRA Query (SMQ) and Preferred Term (PT)

AEs will be summarized according to the Medical Dictionary for Regulatory Activities (MedDRA). The MedDRA version used for reporting will be described in the footnote.

Within each reporting phase (Table 2-5), the following rules are applicable.

- If a subject reported more than one adverse event with the same preferred term, the adverse event with the maximum severity will be presented.
- If a subject reported more than one adverse event within the same primary system organ class, the subject will be counted only once with the maximum severity at the system organ class level, where applicable.

- Statistical analyses performed for the double-blind period will include all post-randomization AEs up to the end of double-blind period irrespective of whether patient was on or off study drug.

The most common adverse events reported ($\geq 2\%$ in any group for each preferred term in the SOC-PT table) will be presented in descending frequency according to its incidence in the LCZ696 group starting from the most common event. Summaries for the double-blind period will be provided for study medication related adverse events, death, serious adverse event, other significant adverse events leading to study discontinuation and adverse events leading to dose adjustment / interruption.

COVID-19 infections will be collected as AEs.

For each reporting period, incidence of AEs will also be listed at a patient level by randomized treatment group including outcome, severity and action taken with the AE.

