5.5.6 Rescue medication

The intent in this study is to ensure that, wherever possible, patients are treated with an evidence-based dose (or lower dose if the target dose is not tolerated) of RAS inhibitor. Some patients in the study may experience intolerable adverse effects thought to be due to study drug which could lead to discontinuation of study medication. If study drug discontinuation is considered despite dose reduction and/or temporary interruption as described in [Section 5.5.5](#), substitution of open-label ACE inhibitor or ARB therapy is recommended, according to the following guidance, to ensure patients receive sufficient RAS blockade.

Hypotension, hyperkalemia, renal dysfunction and cough are likely to be common in the patients enrolled in the present study. Guidance on handling hypotension and hyperkalemia by correcting the underlying causes and/or adjusting the non-disease modifying background therapy is provided to investigators in [Appendix 4](#), and [Appendix 5](#), respectively. If these measures do not lead to resolution of the adverse event(s), the dose of study drug should then be down-titrated or temporarily withdrawn if needed, followed by re-challenge, as described in [Section 5.5.5](#). If a patient experiences symptomatic hypotension (despite the above measures) and a study drug discontinuation is required open-label ACE inhibitor or ARB therapy should be administered and titrated to the guideline-recommended target doses if

tolerated. Similar principles (such as emphasizing dose reduction or discontinuation of non-disease modifying drugs of NSAIDs and diuretics, etc., followed by dose adjustment of study drug) should also be exercised when handling the renal dysfunction adverse events.

Cough is also likely to be a common adverse event in the patients enrolled in the present study because of concomitant lung disease and potentially pulmonary congestion. For patients who have to discontinue study drug per investigator's assessment due to persistent and intolerable dry cough despite dose reduction or temporary interruption/re-challenge of study medication, it is recommended that patients are administered open-label valsartan (titrated to the guideline recommended target dose of 160 mg bid) or an alternative ARB if valsartan is not available.

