
To demonstrate the superiority of LCZ696, compared to ramipril, in delaying the time to new onset of symptomatic HF defined as time-to-first occurrence of HF hospitalization or outpatient HF
	
Time-to-first occurrence of HF hospitalization or outpatient HF (days)
	
Section 2.6

To demonstrate the superiority of LCZ696 compared to ramipril, in delaying the time-to-first occurrence of CV death, non-fatal spontaneous MI^{1,3} or non-fatal stroke⁴
	
Time-to-first occurrence of CV death, non-fatal spontaneous MI^{1,3} or non-fatal stroke⁴ (days).
	
Section 2.6

Objective	Related endpoint and Definition	Analysis method
To demonstrate the superiority of LCZ696, compared to ramipril, in reducing the rate of the composite endpoint of CV death and total (first and recurrent) hospitalizations due to HF, non-fatal spontaneous MI ^{1,3} or non-fatal stroke ⁴	Cumulative number of composite endpoint of CV death and total (first and recurrent) hospitalizations due to HF, non-fatal spontaneous MI ^{1,3} or non-fatal stroke ⁴ (count).	Section 2.6
To demonstrate the superiority of LCZ696, compared to ramipril, in delaying the time to all-cause mortality	Time to all-cause mortality (days).	Section 2.6
To evaluate the safety and tolerability of LCZ696 compared to ramipril	
 • Number and percentage of adverse events, serious adverse events, drug-related discontinuations, etc. • Change from baseline in laboratory assessments and vital signs measurements 	Section 2.7
[REDACTED]	[REDACTED]	[REDACTED]
[REDACTED]	[REDACTED]	[REDACTED]
[REDACTED]	[REDACTED]	[REDACTED]
[REDACTED]	[REDACTED]	[REDACTED]
[REDACTED]	[REDACTED]	[REDACTED]
[REDACTED]	[REDACTED]	[REDACTED]

Objective	Related endpoint and Definition	Analysis method
[REDACTED]	[REDACTED]	[REDACTED]
[REDACTED]	[REDACTED]	[REDACTED]
[REDACTED]	[REDACTED]	[REDACTED]
[REDACTED]	[REDACTED]	[REDACTED]
[REDACTED]	[REDACTED]	[REDACTED]
[REDACTED]	[REDACTED]	[REDACTED]

Objective	Related endpoint and Definition	Analysis method
[REDACTED]	[REDACTED]	[REDACTED]
[REDACTED]	[REDACTED]	[REDACTED]
[REDACTED]	[REDACTED]	[REDACTED]
[REDACTED]		
[REDACTED]	[REDACTED]	[REDACTED]
[REDACTED]	[REDACTED]	[REDACTED]
[REDACTED]	[REDACTED]	Section 2.13.1

Objective	Related endpoint and Definition	Analysis method
[REDACTED]	[REDACTED]	[REDACTED]

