2.1.1 General definitions

Study treatment or drug

In future sections through this document, ‘study treatment’ or ‘study drug’ will be used to refer to investigational therapy assigned to a patient. Specifically, for the double-blind treatment phase, study treatment refers to LCZ696 or ramipril as assigned to a patient at randomization.

Screening epoch or screening period

Screening epoch or screening period is defined as the period starting from date of signed of informed consent until date of randomization or decision on randomization.

Randomized treatment phase

The randomized treatment phase begins at the time of randomization and ends with the last study drug intake or the death of the patient, whichever comes earlier. During the randomized treatment phase, patients will return for scheduled clinic visits. For all related safety analyses randomized treatment starts with the first intake of randomized, double-blind study drug. Temporary interruption of the study drug will not be counted as randomized treatment phase discontinuation.

Post-treatment follow-up phase

The post-treatment follow-up phase (usually after premature permanent study drug discontinuation) begins after last study drug intake + 1 day and ends on the date last seen (or vital status confirmed by indirect contact).

Double-blind period or double-blind treatment epoch

The double-blind period, also called the double-blind treatment epoch, is the combination of the randomized treatment phase and the post-treatment follow-up phase.

Baseline and study day

For analysis purpose, baseline value for all variables is defined to be the last results obtained at or prior to randomization date (or prior to 1st study drug intake for safety assessments). Most of variables will have their baseline at visit 101, unless otherwise specified. [REDACTED]

Study day of any assessment refers to the number of days to the assessment relative to randomization (day 1), or relative to the 1st study drug intake for safety assessments.

Unscheduled visit

Only for the analysis of safety laboratory evaluation will unscheduled measurements be taken into account. For efficacy evaluations, measurements from unscheduled visits will generally not be used, unless specifically specified.

On-treatment data for an efficacy endpoint

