2.6.5 Supportive analysis and sensitivity analysis

Supportive analysis

It is recognized that at the time of the first onset of symptomatic HF event some patients may discontinue randomized treatment and may be prescribed an alternative treatment for HF which could be locally available Entresto™ (sacubitril/valsartan, LCZ696). For the pre-specified secondary endpoints (1), (3) and (5) (numbering refers to Section 2.6.1), the analysis described in [Section 2.6.2](#) will estimate the treatment effect of LCZ696 vs ramipril including any effect of prescribed Entresto™ for ramipril patients who discontinued study drug and took Entresto™ as an alternative treatment. Hence, the following supportive analyses aim to estimate the pure treatment effect as though in a situation whereby Entresto™ was not an available treatment option for HFrEF. In this regard, as a sensitivity analysis, inverse probability of censoring weighted (IPCW) Cox proportional hazards model ([Robins and Finkelstein 2000](#)) will be performed on the secondary endpoints (1), (3) and (5).

Inverse probability of censoring weighted (IPCW) Cox proportional hazards model

In the IPCW analysis, the following censoring mechanism will be used for the event generating process for secondary endpoints:

- For patients randomized to LCZ696 and patients randomized to ramipril but did not take open label Entresto upon diagnosis of HFrEF event will be censored according to the mechanism described for the secondary endpoints.
- For patients randomized to ramipril who subsequently start taking open label Entresto, (defined as treatment switch), censoring will occur at the minimum of the last date the endpoint status was known, the time of death from non-CV causes, 28 days after study treatment discontinuation or start of open-label Entresto.

To adjust for the potential informative censoring, patients in the ramipril arm with event times censored due to treatment switch will be dynamically replaced in the patient risk-set by remaining uncensored patients in the ramipril arm with a matching prognostic profile by up-weighting such patients in the analysis set. At a specific time, patients in the ramipril arm who have not switched to taking open label Entresto will be assigned a weight inversely proportional to the probability of not switching till that time (i.e., patients who do not switch, but have covariates implying a high probability of switching, get a larger weight in the analysis).

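### The SAP commits to between-arm adverse event comparisons only over the whole double-blind period, on or off drug; a supplementary on-treatment comparison should be added

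*SAP*

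**What the plan says.** The secondary safety objective in SAP 1.2 is "To evaluate the safety and tolerability of LCZ696 compared to ramipril". SAP 2.7.1 counts every adverse event after randomization "up to the end of double-blind period irrespective of whether patient was on or off study drug". SAP 2.1.1 states that this period "is the combination of the randomized treatment phase and the post-treatment follow-up phase". The treatment-emergent definition in 2.7.1 has a start (first dose, or worsening after it) but no end.

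For patients who stop study drug because of intolerable effects, Protocol 5.5.6 says that "substitution of open-label ACE inhibitor or ARB therapy is recommended". The supportive efficacy analysis in SAP 2.6.5 allows for an effect of Entresto "for ramipril patients who discontinued study drug and took Entresto™ as an alternative treatment".

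The SAP does limit or adjust for off-drug time in efficacy. SAP 2.1.1 defines on-treatment data with a 28-day window, under a heading that restricts it to efficacy endpoints. SAP 2.5.4 applies it to the primary endpoint, and 2.6.5 adds weighting or truncation for Entresto use.

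Table 2-5 in SAP 2.7.1 assigns adverse events that start after EOT to a separate phase. The accompanying text commits to summaries for screening and for the double-blind period. SAP 2.7.1.1 promises exposure-adjusted AESI rates but does not say which exposure is the denominator.

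**The concern.** Hypotension, hyperkalemia, renal impairment and angioedema plausibly depend on the drug being taken at the time. A whole-period count charges each event to the patient's study-treatment arm, even if it occurs long after stopping or on the other arm's drug class. Two switches cross over in this sense: from LCZ696 to an open-label ACE inhibitor, and from ramipril to open-label Entresto. The whole-period tables alone cannot show whether an event arose on the study drug, on no such drug, or on the comparator's class.

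At stake is how well the safety objective is answered. In a superiority test, including off-drug time usually makes a benefit harder to show. In a safety comparison, the same dilution can make a real excess look smaller.

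**Working it through.** The plan gives no adverse event rate, stopping rate or switching rate, so there is no safety figure to reproduce. What follows is a sensitivity calculation.

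**Inputs**
- Mean follow-up of 19 months (SAP 1.1).
- Proportion p permanently stopping by 19 months: 10, 20 or 30% (assumed), at a constant rate.
- On-drug rate ratio R, LCZ696 to ramipril: 1.3, 1.5 or 2.0 (assumed).

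**Step 1: share of follow-up on drug.** With constant stopping, the on-drug share is a = p / (−ln(1−p)) and the off-drug share is f = 1 − a. For p = 20%, a = 0.20/0.2231 = 0.896 and f = 10.4%. For p = 10%, f = 5.1%. For p = 30%, f = 15.9%.

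**Step 2: whole-period rate ratio, same stopping in both arms.**
- Off-drug rate in both arms equal to the on-drug ramipril rate: aR + f.
- Every stopper takes the other arm's drug (extreme case): (aR + f) / (a + fR).

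For R = 1.5 and p = 20%: 1.5 × 0.896 + 0.104 = 1.448, and 1.448 / (0.896 + 1.5 × 0.104) = 1.377.

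| p | f | R = 1.3: equal / all cross | R = 1.5: equal / all cross | R = 2.0: equal / all cross |
|---|---|---|---|---|
| 10% | 5.1% | 1.285 / 1.265 | 1.475 / 1.438 | 1.949 / 1.855 |
| 20% | 10.4% | 1.269 / 1.231 | 1.448 / 1.377 | 1.896 / 1.718 |
| 30% | 15.9% | 1.252 / 1.195 | 1.421 / 1.316 | 1.841 / 1.589 |

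**Step 3: crude percentages.** The main tables count patients, not events. Assume a cumulative ramipril hazard of 0.10 over 19 months. With R = 1.5 and no stopping, the risk ratio is (1 − e^−0.15)/(1 − e^−0.10) = 0.1393/0.0952 = 1.46. With 20% stopping it is 1.42 (equal off-drug rates) or 1.35 (all cross). The loss is of similar size.

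**Step 4: can the direction reverse?** Take R = 1.00, 30% stopping on LCZ696 and 20% on ramipril, and an off-drug rate k times the on-drug rate in both arms. The ratio is (0.841 + 0.159k) / (0.896 + 0.104k). It is 1.05 for k = 2 and 1.09 for k = 3. With the stopping figures exchanged it is 0.95 and 0.92. Here the rule creates a difference where there is none on drug.

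**Step 5: denominator.** SAP 2.4.1 defines treatment exposure, study drug exposure without interruptions, and overall follow-up. If off-drug events were divided by drug exposure, unequal stopping alone would shift the rate ratio. With R = 1, equal rates on and off drug, and 30% versus 20% stopping, it is (1/0.841)/(1/0.896) = 0.896/0.841, about 1.07.

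**The case against.** **The plan already separates on-drug from off-drug events.** SAP 2.1.1 defines a randomized treatment phase that ends at last intake and gives it a start rule for safety analyses. Table 2-5 splits events at EOT, and later text refers to reporting phases. This stands in part: the apparatus exists, so one cannot say that no separation is made. But the text does not reconcile it with the on-or-off rule or name an output that compares the arms before EOT.

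**Other summaries cover tolerability.** Drug-related events and events leading to dose adjustment or interruption are tabulated and depend little on off-drug time. That helps. But the first relies on investigator causality and the second on a dose action, so neither gives an on-treatment AESI rate.

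**Whole-period counting is legitimate.** It keeps randomized follow-up intact and suits delayed risks such as malignancy or cognitive impairment. On-treatment counts suffer informative censoring, because patients stop for these very events. This stands, and it is why the new tables should be supplementary.

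**Crossover may be rare.** SAP 2.6.5 says only that some patients may be prescribed Entresto; it does not predict that they will be. An ARB is neither arm's study drug. Protocol 5.6.2 requires permanent discontinuation for suspected clinically significant angioedema, so an on-drug case is already counted before any switch. All this stands, and the all-cross column above is an extreme.

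**Limit on the absence claim.** Parts of SAP 2.10 to 2.13 and of the Protocol between 9.5.1 and 9.7 are blacked out. The claim is confined to the readable SAP text.

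**Conclusion.** The gap is real and worth closing, as a cheap improvement. The whole-period analysis is not wrong, but alone it answers the safety objective incompletely for events that follow current drug.

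A reader might infer that the safety comparison is diluted toward no difference. The documents do not support that as a fact, because they give no stopping, switching or off-drug event rates. Dilution is the expected direction for drug-caused events when stopping is similar in the two arms, and it is modest. Unequal stopping combined with higher event rates off drug can push the ratio either way (Step 4).

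A reader might also take the proportion who stop as the share of follow-up off drug. That overstates the effect: with constant stopping, 30% stopping by 19 months gives about 16% off-drug time.

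These sizes rest on constant rates and assumed stopping proportions. They show scale and are not forecasts for this trial.

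**What to change.** Keep the whole-period tables and make three changes to the SAP.

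1. In 2.7.1 and 2.7.1.1, add on-treatment summaries by arm of serious adverse events, AESIs, and adverse events by system organ class and preferred term. Count events from first dose to 28 days after permanent discontinuation (the window 2.1.1 already uses for efficacy), or to the start of open-label ACE inhibitor, ARB or Entresto if earlier. State how open-label use during a temporary interruption is handled.
2. In 2.7.1.1, name the exposure used for each adjusted rate: follow-up time for whole-period events, and the matching on-treatment person-time for on-treatment events.
3. State which outputs use the post-EOT phase of Table 2-5.

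The cost is SAP wording and repeat runs of existing table programs with an on-treatment flag. Stop dates and later open-label medication are already collected and summarized under 2.4.1. The downside is more tables, and a comparison that is no longer randomized after discontinuation and is subject to informative censoring. The new tables should therefore be labelled supportive.

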2.7.1.1 Adverse events of special interest / grouping of AEs

Specific AEs of interest will be summarized separately in addition to the above analysis. These specific AEs of interest are: angioedema (AAC adjudicated), hyperkalemia, hypotension, renal impairment, cognitive impairment, hepatotoxicity, statin drug-drug interaction, anaphylaxis, hypersensitivity, malignancy, embryo-fetal toxicity/lethality and neonatal/infantile toxicity through exposure from breast milk. Besides providing the crude percentages, annualized exposure adjusted incidence rates will also be provided by treatment group.

The search paths for the related preferred terms (PTs), high level group term (HLGT), high level term (HLT), in Standard Medical Queries (SMQs), or NMQ in MedDRA for these risks are stored (or alternatively "summarized") in the latest version of LCZ696 Case Retrieval Strategy.

In addition to above standard analyses, for double blind phase, analysis for time-to-first selected AEs by treatment group will be performed using Kaplan-Meier estimate. The annualized exposure duration adjusted event rates will also be provided.

2.7.2 Deaths

Patients experiencing deaths during the study period will be reported separately for screening epoch and double-blind treatment epoch. Deaths occurring during double-blind treatment epoch will be summarized by actually received treatment group to present number and percentage of patients died by overall and adjudicated reason categories (CV/ non-CV). Separate listings will be provided for patients died during the study period with primary reason of death as confirmed by adjudication committee.

